b) Urine samples (100 µL aliquots) will be centrifuged (10,000 g for 10 min at 4 °C) to remove particulates followed by dilution with water (1:1 to 1:3 vol/vol). Samples (10 µl) will be added to 10 ml of ACN and centrifuged at 3000 g for 15 min. The supernatant will be collected, dried, reconstituted in 500 µl of ethanol (50 % v/v) containing 0.1 % ascorbic acid and (w/v) and transferred to HPLC vials for untargeted analyte detection by high resolution MS (20; 35).

To deplete common matrix interferences such as phospholipids, salts, and proteins and optimize sample preparation each sample supernatant produced in a) and b) may also be loaded to Oasis Prime HLB Cartridges (Waters). Sample preparation methods will be tested.

2) Chromatographic separation and high-resolution mass spectrometry (MS): Triplicates (i.e. technical replicates) of each serum or urine sample will be separated on a Dionex UltiMate 3000 Binary Rapid Separation UHPLC with Diode Array Detector with a reverse phase (RP) C18 column for retention of medium polar and non-polar analytes as well as a hydrophilic interaction chromatography (HILIC) column for retention of highly polar metabolites (35). Separation of samples on RP and HILIC columns prior to MS will provide more comprehensive metabolome coverage. To detect the greatest number of metabolites, gradient elution protocols will be optimized separately for serum and urine samples. Chromatographic separations will be followed by MS using a Thermo Scientific Q Exactive Plus Orbitrap high resolution mass spectrometer. The orbitrap provides high mass accuracy (1–2 p.p.m.), resolution up to 100,000 and dynamic range of 5,000. Data will be collected in both positive and negative ESI modes (mass range of 100–2,000 m/z).

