Quality control (QC): Three kinds of QC samples will be implemented: 1) A standard mixture solution of PAC-derived MM and/or bile acids at a concentration of 1 mg/L; 2) A bulk QC sample made by pooling equal aliquots of each urine or serum sample; 3) Bulk urine or serum QC sample spiked with standard mix. These QC controls will help evaluate retention time stability, peak shape, detector response and mass accuracy. To avoid freeze-thaws QC controls will be prepared, aliquoted, and stored at -80 °C. QC samples will be injected 5 times at the beginning of the run to ensure system equilibration, and then once every 10 samples to monitor stability of analysis. Samples will be randomized to reduce systematic error associated with measurement variability (35).

3) Data processing and metabolite identification: XCMS Online software (<https://xcmsonline.scripps.edu>) will be used to identify and line up MS peaks/metabolites. Background noise will be filtered. A 0.2 min retention time and 0.002 Da mass tolerance window will be applied. Metabolites will be identified using online databases such as Chemspider, METLIN, (<https://metlin.scripps.edu/index.php>), Human Metabolome Database (HMDB) (<http://www.hmdb.ca/>), MZedDB (<http://maltese.dbs.aber.ac.uk:8888/hrmet/index.html>) and Kyoto Encyclopaedia of Genes and Genomes (KEGG) (<http://www.genome.jp/kegg/>). Metabolite profile and identification will be achieved by comparing mass, RT, MS/MS fragmentation patterns in secondary LC-MS/MS analysis, and/or against standard compounds for aglycones. We will look for particular signatures of metabolites that are significantly increased in blood after GP intake (humans) or PAC intake (mice). As many metabolites are likely to be conjugated to glucuronide, sulphate and methyl groups, enzymatic treatments will be applied to release the aglycone for quantification purposes. After enzymatic treatment, samples will be profiled and compared to untreated samples. After deconjugation an increase in the signal of particular aglycones (previously quantified) is expected. The relative increase in these signals coupled with the decrease/disappearance of the conjugated compound will be used to quantify the concentration of these metabolites.

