4) Statistical analysis: To find the bacteria that respond to GP either positively or negatively (i.e. GP responders) we will omit those strains that are found to change with only SPI supplementation. To further understand how the GP responders affect host metabolic health as a group, we will derive a GP Responder

Index (GRI) based on the abundance and diversity [Heip evenness] of the identified bacteria (36). Data will be subject to two-way repeated measures ANOVA to decipher main effects and interactions between GP and SPI. $P < 0.05$ will be considered significant.

To detect significant differences in metabolites MetaboAnalyst 3.0 software (<http://www.metaboanalyst.ca/>) will be used. Principal components analysis (PCA) will transform original data variables into a smaller number orthogonal variables built from linear combinations to explain most of the data variance and cluster samples from each time-point or group to be analyzed. Significant difference ($p < 0.05$) will be determined within subject at different time-points, within group, and between groups. Variable importance in projection (VIP) scores will be estimated to select metabolites biomarkers from a partial least squares-discriminant analysis (PLS-DA). VIP scores are a weighted sum of PLS weights for each variable and measure the contribution of each predictor variable to the PLS-DA model. Compounds with VIP score > 4 represent metabolites with greatest change, which will be chosen for proof of identity. Before carrying out PCA and PLS-DA analyses, peak intensity will be controlled by a logarithmic transformation, and monitored by Pareto scaling. Methods for data preprocessing and statistical analysis will be optimized and additional corrections and tools will be applied as needed (37; 38).

Co-inertia analysis: To aid interpretation of the relationship between the bacterial responders and metabolomics datasets, they will be integrated using a multivariate method known as co-inertia analysis (CIA) (39). We expect to uncover bacterial species/strain level increases and decreases in GP-SPI-supplemented subjects that correlate with a concomitant increase and decrease in production of their metabolites.

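### Metabolite peaks are matched with a fixed 0.002 Da window although mass accuracy is stated in ppm; for heavier ions (above a point between m/z 500 and 2,000, depending on the reading) the window can be narrower than the instrument's stated error

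*Combined protocol and SAP*

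**What the plan says.** All the relevant text is in the Combined protocol and SAP, section 1.3, under the Metabolomics Workflow of the microbiome-wide association study (MWAS).

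- **Item 2 (chromatography and mass spectrometry)** states accuracy in relative terms: "The orbitrap provides high mass accuracy (1–2 p.p.m.), resolution up to 100,000 and dynamic range of 5,000". The scan range is m/z 100–2,000, in both ionisation modes.
- **Quality control** uses a standard mixture, a pooled sample and a spiked pooled sample, injected five times at the start of the run and then once every 10 samples. "These QC controls will help evaluate retention time stability, peak shape, detector response and mass accuracy".
- **Item 3 (data processing)** says that XCMS Online "will be used to identify and line up MS peaks/metabolites". After a sentence on filtering noise comes the rule: "A 0.2 min retention time and 0.002 Da mass tolerance window will be applied". It carries no ± sign, no ppm scaling and no justification, and does not name the step or steps it governs.
- **Identification**, also in item 3, rests on more than mass: "Metabolite profile and identification will be achieved by comparing mass, RT, MS/MS fragmentation patterns in secondary LC-MS/MS analysis, and/or against standard compounds for aglycones".
- **Item 4 (statistical analysis)** leaves general latitude: "Methods for data preprocessing and statistical analysis will be optimized and additional corrections and tools will be applied as needed (37; 38".

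**The concern.** An error stated in ppm grows in proportion to m/z, and the scan range spans a 20-fold range of mass. One absolute window cannot track it: the window is loose at the bottom and may be too tight at the top. Where it is too tight, measurements of one ion in different samples may not be grouped. The ion then appears as two features, each missing in some samples, or fails to match its reference mass.

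A split feature would carry through everything in item 4: the log transformation, PCA, PLS-DA with its VIP cut-off of 4, the within-subject comparisons over time, and the co-inertia analysis with the bacterial data. Urine and serum metabolites are listed among the outcome measures in section 1.6. Because the analysis is partly untargeted and also seeks unknown metabolites (section 1.2), heavy ions cannot be dismissed in advance.

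**Working it through.** The plan gives no derivation of 0.002 Da, so there is no figure of its own to reproduce. The check is a unit conversion.

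**Inputs (section 1.3, items 2 and 3).** Window 0.002 Da; accuracy 1–2 ppm; range m/z 100–2,000.

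**Formulas.**
- Error in Da = m/z × ppm × 10⁻⁶
- Window in ppm = half-width ÷ (m/z) × 10⁶
- Crossover m/z = half-width ÷ (ppm × 10⁻⁶)

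**Error and window by mass.**

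| m/z | Error at 1 ppm (Da) | Error at 2 ppm (Da) | ±0.002 Da in ppm | ±0.001 Da in ppm |
|---|---|---|---|---|
| 100 | 0.0001 | 0.0002 | 20 | 10 |
| 500 | 0.0005 | 0.0010 | 4 | 2 |
| 1,000 | 0.0010 | 0.0020 | 2 | 1 |
| 1,500 | 0.0015 | 0.0030 | 1.33 | 0.67 |
| 2,000 | 0.0020 | 0.0040 | 1 | 0.5 |

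The last column applies if 0.002 Da is the total width.

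**Crossover for one measurement against its true mass.**
- ±0.002 Da, 2 ppm: 0.002 ÷ 0.000002 = m/z 1,000
- ±0.002 Da, 1 ppm: 0.002 ÷ 0.000001 = m/z 2,000, the top of the range, so the window is never narrower than the error
- Total width 0.002 Da, 2 ppm: 0.001 ÷ 0.000002 = m/z 500
- Total width 0.002 Da, 1 ppm: 0.001 ÷ 0.000001 = m/z 1,000

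**Two measurements compared with each other.** If the ppm figure is a hard bound, two readings of one ion can differ by at most twice that bound. Against 0.002 Da, this worst case begins to exceed the window above 0.002 ÷ 0.000004 = m/z 500 at 2 ppm, and above 0.002 ÷ 0.000002 = m/z 1,000 at 1 ppm.

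**Low end.** At m/z 100 the ±0.002 Da window is 20 ppm, or 10 to 20 times the stated error. At m/z 500 it is 4 ppm, or 2 to 4 times.

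**How far assumptions drive any miss rate.** At m/z 2,000 with ±0.002 Da, a single measurement falls outside the window in 50% of cases at 2 ppm and 0% at 1 ppm if the error is uniform within a hard bound. If the ppm figure is instead the standard deviation of a normal error, the rates are 62% and 32%. The documents do not say which applies.

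**The case against.** The strongest reply is that the arithmetic shows a possibility and not a rate.

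- **Precision is not given.** A reader might infer splitting rates by taking two independent errors, uniform within ±2 ppm. With s = m/z × 2 × 10⁻⁶, the share of pairs differing by more than 0.002 Da is (1 − 0.002 ÷ 2s)² where 2s exceeds 0.002 Da, and zero otherwise: 0% at m/z 500, 25% at 1,000, 44% at 1,500 and 56% at 2,000. The documents do not support these as estimates. They state accuracy against true mass, whereas alignment depends on run-to-run scatter. A calibration offset shared by all runs counts against accuracy but cancels between samples. This objection stands.
- **Share of the axis is not share of metabolites.** A reader might also note that (2,000 − 1,000) ÷ (2,000 − 100) = 53% of the scanned range lies above m/z 1,000 and infer that about half the features are at risk. That counts m/z units. The targets named are proanthocyanidin-derived microbial metabolites and bile acids, and none is shown to exceed m/z 1,000. Section 1.2 describes proanthocyanidins as poorly absorbed, while serum and urine are the matrices assayed. This stands too.
- **The low end matters less.** The window is stated just after peak alignment, and identification also uses retention time, fragmentation and standards, so extra candidate identities are a weak complaint.
- **The plan has safeguards.** They help only in part. Identification criteria do not rejoin a feature split at alignment. Quality-control samples evaluate mass accuracy, but no rule ties the result to the tolerance. The promise to optimise preprocessing permits a mass-dependent window without committing to one.

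**Conclusion.** The concern holds as a conditional point. One absolute window is applied where the stated accuracy is relative, so its width in ppm falls from 20 to 1 across the scan range. On the 2 ppm, ±0.002 Da reading it is narrower than the stated error above m/z 1,000; over all four readings the crossover runs from m/z 500 to 2,000. The text settles neither the meaning of the window nor whether the ppm figure is a bound or a typical error.

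It would go too far to say that features will be split, or that m/z 1,000 is the threshold without its conditions: at a hard bound of 1 ppm with ±0.002 Da, no single measurement in the scan range falls outside its window. The number of affected features cannot be determined from the documents.

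The reach is limited to heavier ions in the exploratory MWAS metabolomics. The primary 16S endpoint and the sample size do not depend on this setting, and the listed secondary endpoint for the MWAS is the collection and storage of samples. This is a desirable refinement, worth making because it is almost free.

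**What to change.** In section 1.3, Metabolomics Workflow, item 3, replace the fixed mass window with one in ppm. State whether it is ± or total width, and whether it covers alignment, database matching or both. ±5 ppm is a reasonable example, not a value derived from the plan. It equals ±0.0005 Da at m/z 100 and ±0.01 Da at m/z 2,000, so it is tighter than ±0.002 Da below m/z 400 (0.002 ÷ 0.000005) and wider above.

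Confirm or widen it from the observed mass spread in the pooled and spiked quality-control injections already planned. If 2 ppm is a hard bound, ±5 ppm covers the largest difference between two readings, 4 ppm. If 2 ppm is the standard deviation of independent normal errors, the difference has standard deviation 2 × √2 = 2.83 ppm and about 8% of pairs would still exceed 5 ppm, so the check matters.

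An absolute floor is optional. A floor of 0.0005 Da would have no effect, since ±5 ppm already equals it at m/z 100. A floor of 0.001 Da would bind below m/z 200 and leave 10 ppm at m/z 100.

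The cost is one sentence and a software setting, with no new samples or runs.

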The proposed study will first investigate how short-term supplementation with GP-SPI may modify the gut microbial community in healthy participants while monitoring liver and kidney function/health. We will also perform a longitudinal, microbiome-wide association study (MWAS) to identify gut bacteria species/strains that are positively or negatively associated with GP-SPI supplementation. Metabolomics analysis will be performed on collected urine and blood samples to identify/quantify known and unknown metabolites. Shotgun metagenomic sequencing will be performed on fecal samples to generate high quality draft genomes for species/strain level identification. These dynamic data sets will serve as input for the MWAS to correlate increasing/decreasing levels of gut bacterial species/strains to increasing/decreasing metabolites in blood and urine. These bacteria-metabolite associations will then be used to infer cause-effect relationships that can be further tested *in vitro*. We expect that successful completion of these studies will contribute to mechanistic explanations for how dietary polyphenols such as grape PACs alter the gut microbiota and resulting MM to promote metabolic health.

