1.3 Research Design and Methods

Overview

This is a pilot time course study to characterize the effect of GP-SPI on the gut (i.e. fecal) bacterial community of healthy subjects. Following screening, enrolled subjects will washout of PAC-rich foods for 5 days while also consuming SPI. Subjects will then consume GP-SPI over a 10-day supplementation period. Fecal, urine, and blood samples will be collected. Comprehensive metabolic panel (CMP) tests performed before and after the GP-SPI supplementation period will monitor liver and kidney health. Using deidentified fecal, urine, and blood samples collected from time course study a MWAS study (funded by R01 AT010242-01) will be performed.

Successful completion of this pilot study will yield data that will inform the design of a follow-up placebo-controlled intervention study, which will be described in a separate clinical protocol that will be submitted to IRB for approval.

A. Research Procedures

[figure not shown]

Figure 1. Clinical Study Design

Location

Screening and out-patient visits will take place in the Surgery Clinic in the Clinical Academic Building (CAB) or Surgery Department (MEB 5) and NJ Institute of Food Nutrition and Health (IFNH).

Recruitment

Prospective participants will be recruited through flyers posted locally on Rutgers University campuses and sent to university email lists (**Flyer** attached). Interested subjects will call in or email to receive further information about the study. A member of the study team will give a brief summary of the study. If the subject requests a screening appointment, the investigator will ask for verbal consent to proceed with a list

of questions (**Telephone Script** attached). Collecting this information at this time assists in expediting the paperwork during the visit and spares ineligible subjects the inconvenience of a futile appointment.

Eligibility Screening

At the screening visit (at IFNH), a member of the study team will explain the study in detail to the subject. Full explanation of study procedures and potential risks will be provided. The subject will have ample time to read the Consent and ask questions before signing and proceeding with screening procedures. A signed copy of Consent form (form attached) will be given to the subject.

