After consent a participant ID will be assigned to subject. Demographics, medical history, height, and weight (**Demographics** and **Medical History** forms attached) will be recorded for each subject. Females will be given a urine-based pregnancy test onsite and result will be recorded. If inclusion criteria are met at this time, subject will be asked to schedule a visit at CAB with study nurses for a blood draw to perform CMP screening test. If CMP results are within normal range the subject will be enrolled and return to IFNH to receive study materials needed for participation in the study. If any CMP values are outside normal ranges subject will be advised that they do not fulfill all eligibility criteria, they will be given a copy of their CMP results, and if necessary, advised to see their primary care provider. All screened subjects will be documented on **Screening and Enrollment Log** (attached).

The final selection will be contingent upon the individuals meeting all eligibility criteria and deemed capable of complying with the study protocol.

Study Procedures

- Thirty subjects will be enrolled.
- **Food List:** Participants will maintain their usual diet except for a provided list of PAC-rich foods that they will be asked to abstain from for a 5-day wash-out period and during the 10-day intervention. The Food List is provided below. The goal is to have GP-SPI as the main/only source of PAC in the diet for the study period.
- **Wash-out and SPI (Day -5 through -1):** On day -5 (pre-baseline) before any supplementation, each subject will collect their fecal and urine sample. Each subject will then consume SPI twice a day (provided as pre-weighed packets of 20 g) during a 5-day wash-out period (days -5, -4, -3, -2, and -1). Subjects will be instructed to mix each packet of SPI in 250 mL of water or in a smoothie (recipe example below will be provided) using allowed foods as detailed in instructions and consume once in the morning before breakfast and once in the evening before dinner.

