- **Day 0:** On the following day each subject will collect their baseline (day 0) stool and urine samples (Fig. 1). They will visit the CAB building to have a blood sample (2 tablespoons or 30 mL) drawn by a study nurse. Blood will be used for CMP test and prepared serum will be aliquoted and stored at -80 °C until processing for marker analysis and metabolomics. Analysis of day 0 samples should help isolate any effects due to SPI alone from subsequent samples collected during GP-SPI intervention. On day 0 subjects will drop off urine and stool samples at IFNH and collect GP-SPI packets. On Day 0 participants will also take a break from consuming SPI and will start GP-SPI supplementation on morning of Day 1.
- **GP-SPI (Day 1 – 10):** Each subject will receive twenty pre-weighed 20 g packets of GP-SPI. On day 1 subjects will be instructed to mix each packet of GP-SPI in 250 mL of water or in smoothie (recipe example will be provided, please see below) using allowed foods as detailed in instructions and consume the GP-SPI mix once in the morning before breakfast and once in the evening before dinner for 10 consecutive days (Fig. 1).

- Subjects will be provided with a personal blender for smoothie preparation (value ~ \$25) that they can keep.
- **Digital food diary:** Participants will be asked to take photos of all their food and drink (except water) including the study supplements with their personal mobile computing device (e.g. smart phone, iPad, or similar). Participants will be required to download the free mobile app WhatsApp to send photos with a brief description of the food items. Photos and food description may also be sent to an email address that will be created for this study ([contact]). The food diary must be kept over the 5-day SPI and wash-out period, day 0 (break day), the 10-day GP-SPI intervention period, and up until the final blood draw on day 11 (17 days total).

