1.6 Study Variables

A. Independent Variables, Interventions, or Predictor Variables

The independent variables will be supplementation with SPI or GP-SPI.

B. Dependent Variables or Outcome Measures

Outcome measures are gut microbial community analyses, CMP results, urine and serum metabolites, and bacterial genes, species/strains.

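### The MWAS omission rule attributes to SPI a change that is SPI plus PAC withdrawal, and can drop strains that reverse on GP-SPI (minor, exploratory MWAS only)

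*Combined protocol and SAP*

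**What the plan says.** Section 1.3, Overview, gives the lead-in: "enrolled subjects will washout of PAC-rich foods for 5 days while also consuming SPI". Study Procedures in the same section say the same from both sides. Subjects keep their usual diet except for "a provided list of PAC-rich foods that they will be asked to abstain from for a 5-day wash-out period" and through the GP-SPI period. On day -5, "before any supplementation, each subject will collect their fecal and urine sample", and SPI is then taken twice daily on days -5 to -1. Day 0 is a break day with the baseline samples, and GP-SPI runs from day 1 to day 10.

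On the purpose of the day 0 sample the plan says: "Analysis of day 0 samples should help isolate any effects due to SPI alone from subsequent samples collected during GP-SPI intervention". Section 1.6 adds: "The independent variables will be supplementation with SPI or GP-SPI". The diet restriction is not listed there.

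The MWAS statistical analysis (section 1.3, Metabolomics Workflow, item 4) looks for bacteria that respond to GP in either direction and states that "we will omit those strains that are found to change with only SPI supplementation". The responders then go into the GRI and are integrated with the metabolomics data by co-inertia analysis. The same paragraph names a two-way repeated measures ANOVA with significance at P < 0.05, but does not expressly tie it to the omission step.

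**The concern.** The rule is meant to remove strains whose movement is due to the soy carrier and not to the grape polyphenols. That works only if the window it uses contains SPI and nothing else. Here the window also contains the withdrawal of foods rich in the compounds that the Food List in section 1.3 describes as major actives of GP-SPI. A PAC-sensitive strain could fall when those foods stop and rise when GP-SPI supplies PACs again. It would be a genuine GP responder, yet its fall counts as a change in the SPI window. As worded, the rule has no exemption for a change in the opposite direction.

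Two things are at stake. First, readers would take the omitted strains to be SPI effects, which the design cannot show. Second, the MWAS aim in section 1.2 is "to identify gut bacteria species/strains that are positively or negatively associated with GP-SPI supplementation", and a responder removed at this step is lost to the GRI and the co-inertia analysis.

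**Working it through.** **What each sample contrast contains**

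| Contrast | SPI | PAC-rich foods | GP-SPI |
|---|---|---|---|
| Day -5 (before any SPI) to day 0 | started | stopped | none |
| Day 0 to days 2-10 | carrier only, as part of GP-SPI | still restricted | started |

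The plan has no SPI period on usual diet, no wash-out without SPI and no SPI arm. The first contrast is therefore SPI plus PAC withdrawal, and nothing in the data can divide it. The withdrawal is partial, because the Food List allows one serving a day from a list of low-PAC foods.

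**What the rule does to a reversing strain**

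- *Reading A: a strain that changes in the SPI-only window is omitted.* A strain that falls and then rises is dropped. The day 0 wording in section 1.3, which speaks of effects of SPI alone, supports this reading.
- *Reading B: a strain that changes under SPI and not under GP-SPI is omitted.* The reversing strain is kept. The rule then removes only strains that are not GP responders anyway.

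**Size under reading A (illustration)**

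The plan gives no figure for this step, so there is none to reproduce. Inputs:

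- Completers: 30 less 20% = 24 (section 4.3).
- GP rise: (0.4% - 0.1%)/0.5% = 0.6 SD (section 1.5, planning values for *A. muciniphila*).
- Two-sided paired tests at 0.05. The sidedness is from section 6.1. Using this test for the omission step is an assumption.
- Within-subject correlation r of 0.5 or 0.8, the same between all visits, and a withdrawal fall of 0, 0.15 or 0.30 SD. These are assumptions.

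The SD of a change is SD x √(2(1 - r)), which is 1.00 SD at r = 0.5 and 0.632 SD at r = 0.8. The noncentrality of the paired t (23 df) is fall x √24 / √(2(1 - r)), with the fall in SD units:

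- r = 0.5: a fall of 0.15 gives 0.735, so P(omitted) = 10.9%; a fall of 0.30 gives 1.470, so 29.1%.
- r = 0.8: a fall of 0.15 gives 1.162, so 20.0%; a fall of 0.30 gives 2.324, so 60.5%.
- GP rise of 0.6: 2.939 gives 80.4% detected at r = 0.5; 4.648 gives 99.4% at r = 0.8.

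The two changes share the day 0 sample and are correlated (-0.5 under this model), so the joint result was simulated for days -5, 0 and 10, without false discovery rate (FDR) control:

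| Fall | r = 0.5: detected and kept | r = 0.5: share of detected omitted | r = 0.8: detected and kept | r = 0.8: share of detected omitted |
|---|---|---|---|---|
| 0 | 77% | 4% | 94-95% | 5% |
| 0.15 SD | 70% | 13% | 79% | 20% |
| 0.30 SD | 53% | 34% | 39% | 61% |

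Without the omission, 80% and 99% are detected.

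The falls can be put on the plan's own scale, with a day 0 mean of 0.1% and SD 0.5%. A fall of 0.15 SD is 0.075 points (0.175% to 0.10%, a 43% drop). A fall of 0.30 SD is 0.15 points (0.25% to 0.10%, a 60% drop). No part of the documents supports a drop of either size.

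**Two checks on the alternative of not omitting**

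- A strain that dips 0.3 SD in the wash-out and recovers with no GP effect is kept about 29% of the time without the omission, against 14% with it (r = 0.5). At r = 0.8 the figures are 60% against 16%.
- Among null strains with a chance change in the GP-SPI period, about 89-90% show a window change of opposite sign. A reversal alone is therefore not evidence of a PAC effect.

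**The case against.** The strongest reply is that the rule is a defensible choice of specificity in an exploratory workflow. The dip-and-recover figures bear this out: dropping the rule lets in more strains with no GP effect. That stands, and it is why both lists should be shown instead of replacing one with the other.

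Several further points stand and limit the concern:

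- Reading B is possible, and under it no reversing strain is lost. The documents favour reading A but do not settle the matter.
- A reader might infer that the plan has no test or threshold at all. It does name an ANOVA at P < 0.05 in the same paragraph; what is missing is the link to the omission step.
- A reader might infer that a dropped strain is never analysed. Section 6.1 compares baseline with follow-up for gut microbiota populations, and section 1.6 counts species and strains as outcomes. The strain-level change from day 0 is therefore still compared.
- A reader might take "These bacteria-metabolite associations will then be used to infer cause-effect relationships" as a causal claim about GP-SPI. It concerns links between bacteria and metabolites, and the sentence goes on to say that they would be tested further *in vitro*.
- The day 0 sentence is hedged, and day 0 is a sound baseline for the later samples. Only the attribution to SPI alone fails.
- The illustration treats abundance as normal, applies one organism's planning values to every strain, and uses one GP-SPI visit where five are planned.

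None of this removes the confounding of SPI with PAC withdrawal, which is fixed by the schedule.

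**Conclusion.** The day -5 to day 0 window is SPI plus partial PAC withdrawal, and the plan is wrong to treat it as SPI alone. Confidence in this is high. On the more natural reading of the rule, a strain that moves one way on withdrawal and the other way on GP-SPI can be lost from the responder list, the GRI and the co-inertia analysis.

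Confidence does not extend to how many responders are lost. With no withdrawal effect the loss is about 4-5% of detected responders, which is ordinary test error. The 13-34% (correlation 0.5) and 20-61% (correlation 0.8) rest on assumed falls of 0.15 to 0.30 SD, 24 completers, a GP rise of 0.6 SD and no FDR control. A reader might infer that the rule does discard a third or more of true responders. The documents do not support that, because nothing in them shows that a 5-day partial withdrawal lowers any strain.

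Nor do they support reading this as a threat to the main result. The primary 16S endpoint does not use the rule, the listed secondary endpoint is to collect and store samples for the MWAS, and section 1.3 presents the workflow as an example. Severity is minor and confined to the exploratory MWAS.

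**What to change.** 1. In the day 0 paragraph and in the MWAS statistical analysis (both section 1.3), call the day -5 to day 0 change *SPI plus PAC withdrawal*. Do not describe omitted strains as SPI effects.
2. State which reading of *only SPI* is meant. State that the omission test is the two-sided within-subject contrast of day -5 with day 0 from the repeated-measures model, at 0.05.
3. Define GP responders by the change from day 0 over the GP-SPI period.
4. Report the responder list, the GRI and the co-inertia analysis both with and without the omission. For each strain, show the signed window change with its interval.
5. Put reversing strains in a separate block, and do not label it PAC-restoration responders, because both changes share the day 0 sample.

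The cost is some wording and one further run of three exploratory outputs, with no new samples or visits. The downside is that the list without the omission admits more dip-and-recover strains, which is why neither list should stand alone. The change does not separate SPI from PAC withdrawal; that is for the placebo-controlled follow-up announced in section 1.3.
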